2.3.1.2.2 Freedom from all-cause mortality and MV reintervention at 12 months

The Tendyne device may reduce the risk for surgical reintervention and subjects in the Treatment group are expected to experience greater reduction in MR severity than subjects in the Control group. The proportion of subjects alive and without MV reintervention at 12 months will be compared between the Treatment and Control groups.

The null and alternative hypotheses are stated as:

$$H_0: \pi_D - \pi_C \leq -d$$

$$H_1: \pi_D - \pi_C > -d$$

where π_D and π_C are the true event rates for the composite of freedom from all-cause mortality and MV reintervention at 12 months in the Treatment and Control group, respectively, and d is the non-inferiority margin of 10%.

using a one-sided test with a 2.5% significance level, as described above in [Section 2.3.1.1](#).

2.3.1.2.3 Improvement in KCCQ by at least 10 points at 12 months from baseline

To evaluate the benefit of the Tendyne device, the improvement in Quality of Life as measured by change in the KCCQ scores at 12 months from baseline will be compared between the Treatment and Control

Statistical Analysis Plan

groups.

The null and alternative hypotheses are stated as:

$$H_0: P_D - P_C \leq -d$$

$$H_1: P_D - P_C > -d$$

where P_D and P_C represent the proportion of subjects who improve at least 10 points in KCCQ score at 12 months from baseline in the Treatment and Control groups, respectively, and d is the non-inferiority margin of 15%. [REDACTED]

[REDACTED]

[REDACTED]

2.3.1.2.4 Proportion of Patients with NYHA Functional Classification I or II at 12 months

To evaluate improvement in heart failure symptoms, the proportion of NYHA Functional Classification I or II at 12 months will be compared with that at baseline.

The null and alternative hypotheses are stated as:

$$H_0: P_D - P_C \leq -d$$

$$H_1: P_D - P_C > -d$$

where P_D and P_C represent the proportion of subjects with NYHA Classification I/II at 12 months for treatment and control, respectively, and d is the non-inferiority margin of 15%. [REDACTED]

[REDACTED]

[REDACTED]

2.3.1.2.5 Improvement in Six-Minute Walk Test Distance by at least 50 meters at 12 months from baseline

To evaluate the benefit of the Tendyne device, the increase in the Six-Minute Walk Test distance will be compared between the Treatment and Control groups.

The null and alternative hypotheses are stated as:

$$H_0: P_D - P_C \leq -d$$

$$H_1: P_D - P_C > -d$$

Statistical Analysis Plan

where P_D and P_C represent the proportion of subjects increasing their Six-Minute Walk Test distance by at least 50 feet from baseline at 12 months in the Treatment and Control groups, respectively, and d is the non-inferiority margin of 15%. [REDACTED]

[REDACTED]

[REDACTED]

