#### Proportion of Patients with NYHA Functional Classification I or II at 12 months

To evaluate improvement in heart failure symptoms, the proportion of NYHA Functional Classification I or II at 12 months between Tendyne and MitraClip groups will be tested for non-inferiority.

The null and alternative hypotheses are stated as:

$$H_0: P_D - P_C \leq -d$$

$$H_1: P_D - P_C > -d$$

where  $P_D$  and  $P_C$  represent the proportion of subjects who have NYHA Functional Classification I/II at 12 months in the Treatment and Control groups, respectively, and  $d$  is the non-inferiority margin of 15%. [REDACTED] at one-sided 2.5% significance level. [REDACTED]

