#### Improvement in Six-Minute Walk Test Distance by at least 50 meters at 12 months from baseline

To evaluate the benefit of the Tendyne device, the change from baseline in distance walked as measured by the 6MWT will be compared between Tendyne and MitraClip groups at 12 months for non-inferiority.

The null and alternative hypotheses are stated as:

$$H_0: P_D - P_C \leq -d$$

$$H_1: P_D - P_C > -d$$

where  $P_D$  and  $P_C$  represent the proportion of subjects who improved at least 50 meters in 6MWT distance at 12 months from baseline in the Treatment and Control groups, respectively, and  $d$  is the non-inferiority margin of 15%.

at one-sided 2.5% significance level. The justification of the non-inferiority margin  $d$  of 15% is provided in the SAP.

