1.4.2 Secondary Endpoints

For the Randomized Cohort, the secondary endpoints are:

- Freedom from MR > mild (1+) in severity at 30 days post index procedure among survivors
- Freedom from all-cause mortality and mitral valve (MV) reintervention at 12 months post index procedure
- Improvement in Quality of Life (QoL), as measured by the Kansas City Cardiomyopathy Questionnaire (KCCQ) by at least 10 points at 12 months from baseline
- Proportion of Patients with New York Heart Association (NYHA) Functional Classification I or II at

Statistical Analysis Plan

12 months

- Improvement in distance walked on the 6 Minute Walk Test (6MWT distance or 6MWD) by at least 50 meters at 12 months from baseline

For the Non-Repairable Cohort, the secondary endpoints are:

- Change in QoL, as measured by the KCCQ from baseline at 6 months and 12 months
- Improvement of NYHA Functional Classification I or II at 12 months
- Change in 6MWD from baseline at 6 months and 12 months

For the Severe MAC Cohort, the secondary endpoints are:

- Freedom from MR > mild (1+) in severity at 30 days post index procedure among survivors
- Change in QoL, as measured by the KCCQ from baseline at 6 months and 12 months
- Improvement of NYHA Functional Classification I or II at 12 months
- Change in 6MWD from baseline to 6 months and 12 months

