2.11.1 Multiplicity – Randomized Cohort

For the Randomized cohort, hypothesis testing is planned for one primary endpoint and five secondary endpoints. If the primary endpoint is met, secondary endpoints will be evaluated for labeling claims. The first two and the group of the last three secondary endpoints will each be tested at the one-sided significance level of 2.5% and sequentially in the following order:

Statistical Analysis Plan

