7.0 APPENDICES

APPENDIX I. JUSTIFICATION OF NON-INFERIORITY MARGIN AND PERFORMANCE GOAL IN THE HYPOTHESIS TESTS

A. Randomized Cohort: Non-inferiority Margin for Primary Endpoint

A high-contrast, black and white image showing a series of horizontal bars. The bars are thick and black, set against a white background. The bars are positioned at different heights and widths, creating a layered effect. The image is oriented vertically, with the bars running horizontally across the frame.

Statistical Analysis Plan

B. Randomized Cohort-Secondary Endpoints:

Non-inferiority Margin for Freedom from All-cause Mortality and MV reintervention at 12 months

Non-inferiority Margin for Improvement in KCCQ by at least 10 points at 12 months from baseline; NYHA I/II at 12 months and Improvement in 6MWD by at least 50 meters at 12 months from baseline

Statistical Analysis Plan

C. Non-Repairable Cohort: Performance Goal for the Primary Endpoint

Statistical Analysis Plan

D. Severe MAC Cohort: Performance Goal for the Primary Endpoint

[REDACTED]

[REDACTED]

[REDACTED]

E. Severe MAC Cohort-Secondary Endpoints

Performance Goal for Freedom from MR > mild (1+) at 30 days post procedure

[REDACTED]

Statistical Analysis Plan

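### SAP 2.3.1.2.5 defines the randomized-cohort 6-minute-walk responder with a threshold in feet, while its own heading, the rest of the SAP and the protocol use 50 meters

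*SAP*

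**What the plan says.** The endpoint is a responder proportion in the Randomized cohort, compared between Tendyne and MitraClip for non-inferiority with a 15% margin. The relevant texts are:

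- SAP 2.3.1.2.5, heading: "2.3.1.2.5 Improvement in Six-Minute Walk Test Distance by at least 50 meters at 12 months from baseline".
- SAP 2.3.1.2.5, definition of P_D and P_C under that heading: "the proportion of subjects increasing their Six-Minute Walk Test distance by at least 50 feet from baseline at 12 months".
- SAP 1.4.2, endpoint list: "Improvement in distance walked on the 6 Minute Walk Test (6MWT distance or 6MWD) by at least 50 meters at 12 months from baseline".
- SAP Appendix I.B, heading for the margin justification: "Improvement in 6MWD by at least 50 meters at 12 months from baseline".
- Protocol 10.2.1, definition of P_D and P_C for the same hypotheses and margin: "the proportion of subjects who improved at least 50 meters in 6MWT distance at 12 months from baseline".

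The protocol summary and protocol 3.2 also say 50 meters. So does the functional-status element of MVARC Patient Success in protocol Appendix II.

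On the role of the endpoint, SAP 2.11.1 states: "The first two and the group of the last three secondary endpoints will each be tested at the one-sided significance level of 2.5" percent. SAP 2.3.1.2 says the secondary endpoints are evaluated for labeling claims once the primary endpoint is met.

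**The concern.** The odd unit is in the sentence that fixes what is tested, in the document that analysts program from. If it is coded as written, the test uses a different responder endpoint from the one named in the claim. The 15% margin, which Appendix I.B attaches to the 50-meter endpoint, would then be applied to something else.

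There is also a question of timing. While two thresholds stand in the approved text, choosing between them after the data are seen can be challenged as data-driven, even when the choice is the obvious one.

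A separate and much smaller slip is in the section just before. The introductory sentence of SAP 2.3.1.2.4 says "the proportion of NYHA Functional Classification I or II at 12 months will be compared with that at baseline". The hypotheses and definitions below it compare the two arms, and protocol 10.2.1 agrees: "the proportion of NYHA Functional Classification I or II at 12 months between Tendyne and MitraClip groups will be tested for non-inferiority". That slip cannot change the test and adds no weight here.

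**Working it through.** **Text comparison.** Of the visible statements of this threshold, one is in feet and all the others are in meters. The sentence in feet is complete and legible, so neither blacked-out text nor page extraction explains it. The other two tested cohorts analyze mean change in walk distance (SAP 2.3.2.2 and 2.3.3.2) and have no threshold.

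**Conversion.** 50 ft × 0.3048 = 15.24 m. The ratio is 50 / 15.24 = 3.28.

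**Inputs for size.** From the documents: about 382 subjects randomized 1:1, so 191 per arm (SAP 1.3); margin 0.15 (SAP 2.3.1.2.5); one-sided 2.5% (protocol 10.2.1, SAP 2.11.1). No mean, SD, expected responder rate or power is visible for this endpoint, so there is no plan figure to reproduce. The means and SDs below are assumptions.

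**Responder rate in one arm.** For a normal change, rate = 1 − Φ((threshold − mean)/SD). With mean 30 m and SD 80 m:

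- at 50 m: 1 − Φ(0.25) = 0.401
- at 15.24 m: 1 − Φ(−0.1845) = 0.573

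| Mean (m) | SD (m) | Rate at 50 m | Rate at 50 ft | Difference | × 191 |
|---|---|---|---|---|---|
| 20 | 80 | 0.354 | 0.524 | 0.170 | 32 |
| 20 | 120 | 0.401 | 0.516 | 0.115 | 22 |
| 30 | 80 | 0.401 | 0.573 | 0.172 | 33 |
| 30 | 120 | 0.434 | 0.549 | 0.115 | 22 |
| 40 | 80 | 0.450 | 0.622 | 0.171 | 33 |
| 40 | 120 | 0.467 | 0.582 | 0.115 | 22 |

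Results for SD 100 m lie between these. The counts assume that all 191 subjects have a 12-month walk test. If 80% did (an assumption), they would be 0.8 × 22 = 18 to 0.8 × 33 = 26.

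**Effect on the test.** The visible text does not show the test statistic, so I used an unpooled Wald approximation: P(non-inferiority) = Φ((P_D − P_C + 0.15)/SE − 1.96), with SE² = [P_D(1 − P_D) + P_C(1 − P_C)]/191. Missing data, and multiplicity within the group of three endpoints, are ignored.

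*Equal SDs.* Control mean 20, 30 or 40 m; SD 80, 100 or 120 m; Tendyne shortfall 0, 10 or 20 m. Going from 50 m to 50 ft:

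- The Tendyne deficit changes by −0.06 to +1.14 percentage points.
- P(non-inferiority) changes by −9.3 to +1.8 points.
- Both the largest deficit change and the largest fall in probability occur at means 20 v 0 m and SD 80 m. There the deficit goes from 8.78 to 9.93 points and the probability from 0.261 to 0.168.
- With no shortfall the probability changes by −3.0 to +1.8 points.

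*Unequal SDs, both means 30 m.*

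| SD Tendyne / control (m) | P_D − P_C at 50 m | P_D − P_C at 50 ft | P(NI) at 50 m | P(NI) at 50 ft |
|---|---|---|---|---|
| 80 / 120 | −0.033 | +0.024 | 0.644 | 0.930 |
| 120 / 80 | +0.033 | −0.024 | 0.951 | 0.697 |
| 95 / 105 | −0.008 | +0.006 | 0.804 | 0.866 |

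**The case against.** The best reply is that nobody would be misled. One word disagrees with the heading directly above it, with the endpoint's own name, and with a complete definition in protocol 10.2.1. A programmer who codes 50 feet has to overlook all three. I accept that this makes literal use unlikely, and it is why the point ranks no higher than a correction that should be made.

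The second reply is that the size figures rest on invented distributions. That is true. The largest swings need a 1.5-fold difference in SD that nothing in the documents supports; at 95 v 105 m the shift is about 6 points. The 9-point fall occurs only where non-inferiority is already improbable. The effect on the test therefore cannot be determined from the documents. The rise in responder rates is firmer: a lower threshold cannot give fewer responders, and any label would report those rates.

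Third, the position in the testing sequence is partly inferred. SAP 2.11.1 refers to a last group of three, but the list that follows is not visible. I place the walk test in that group from the order in SAP 1.4.2 and 2.3.1.2. Nor is that group the last test of all, since SAP 2.3.1.1 puts superiority on the primary endpoint after the secondary endpoints.

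None of this removes the contradiction.

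**Conclusion.** The concern holds. SAP 2.3.1.2.5 contradicts its own heading and every other visible statement of the threshold, in the sentence that defines the tested proportions. Read literally, it lowers the threshold by a factor of 3.28.

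Under the assumed distributions, responder rates rise from 35–47% to 52–62%. The test result barely moves if the arms have equal spread and little or no shortfall. It can move materially, in either direction, if their spreads differ. The direction therefore cannot be predicted in advance.

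The consequence is confined to one secondary labeling claim in the Randomized cohort. The primary endpoint, sample size, trial success and the other cohorts do not depend on it. The contradiction itself is certain. Its numerical effect is conditional on assumptions that the documents neither support nor rule out. Agreement of all the other statements could be checked only in the visible text, because the body of Appendix I is blacked out.

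**What to change.** Before the analysis, replace feet with meters in the definition of P_D and P_C in SAP 2.3.1.2.5. All visible statements then agree at 50 m.

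In the same revision, as an editorial correction, reword the introductory sentence of SAP 2.3.1.2.4 so that the NYHA proportion is compared between the Treatment and Control groups, in line with its stated hypotheses and protocol 10.2.1.

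The cost is one word and one phrase. No new data are needed, and the margin, significance level and sample size stay as they are.

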2.3.2 Non-Repairable Cohort

2.3.2.1 Non-Repairable Cohort – Primary Endpoint

The primary endpoint for the Non-repairable cohort is freedom from all-cause mortality and heart failure hospitalization at 12-months post the index procedure. The trial is intended to demonstrate that the primary endpoint event rate in subjects treated with the Tendyne™ Transcatheter Mitral Valve System does not exceed a pre-specified performance goal.

The null and alternative hypotheses are:

$$H_0: \pi_D \leq \pi_{PG}$$

$$H_1: \pi_D > \pi_{PG}$$

where π_D is the true event rate of freedom from all-cause mortality and heart failure hospitalizations at 12-months post the index procedure, and π_{PG} is the performance goal. The performance goal (PG) is set at 45% (Justification of the PG is provided in the Appendix). [REDACTED]

[REDACTED]

The null hypothesis will be tested at the one-sided 2.5% level of significance [REDACTED].

[REDACTED]

The primary analysis population for the primary endpoint is the AP population. The primary endpoint will be considered met if the null hypothesis is rejected.

2.3.2.2 Non-Repairable Cohort – Secondary Endpoints

The following secondary endpoints will be evaluated. These endpoints will be evaluated for labeling claims if the primary endpoint for the Non-repairable cohort is met. The primary analysis population for the secondary endpoint of the Non-repairable cohort is the AP population.

Statistical Analysis Plan

2.3.2.2.1 Change in KCCQ from Baseline at 12 months

To evaluate the benefit of the Tendyne device, the Quality of Life as measured by the KCCQ scores at 12 months will be compared with those from baseline.

The null and alternative hypotheses are:

$$H_0: D_{12M} \leq 0$$

$$H_1: D_{12M} > 0$$

Where D_{12M} is the average change in KCCQ score from baseline at 12 months. [REDACTED]

[REDACTED] one-sided 2.5% significance level.

[REDACTED]

2.3.2.2.2 Improvement of NYHA Functional Classification I or II at 12 months

The proportion of subjects with NYHA Functional Classification I or II at 12 months will be evaluated at two-sided 5% level of significance [REDACTED].

The null and alternative hypotheses are stated as:

$$H_0: P_{M12} = P_B$$

$$H_1: P_{M12} \neq P_B$$

where P_{M12} and P_B represent the proportion of NYHA Classification I or II at 12 months and baseline, respectively.

[REDACTED]

2.3.2.2.3 Change in Six-Minute Walk Test Distance from Baseline at 12 months

To evaluate the benefit of the Tendyne device, the distance walked at 12 months as measured by the 6MWT will be compared with those from baseline.

The null and alternative hypotheses are:

$$H_0: D_{12M} \leq 0$$

$$H_1: D_{12M} > 0$$

Where D_{12M} is the average change in 6MWT distance from baseline at 12 months. [REDACTED]

[REDACTED] one-sided 2.5% significance level.

[REDACTED]

Statistical Analysis Plan

2.3.2.2.4 Change in KCCQ from Baseline at 6 months

To evaluate the benefit of the Tendyne device, the Quality of Life as measured by the KCCQ scores at 6 months will be compared with those from baseline.

The null and alternative hypotheses are:

$$H_0: D_{6M} \leq 0$$

$$H_1: D_{6M} > 0$$

Where D_{6M} is the average change in KCCQ score from baseline at 6 months.

at the one-sided 2.5% significance level.

2.3.2.2.5 Change in Six-Minute Walk Test Distance from Baseline at 6 months

To evaluate the benefit of the Tendyne device, the distance walked at 6 months as measured by the 6MWT will be compared with those from baseline.

The null and alternative hypotheses are:

$$H_0: D_{6M} \leq 0$$

$$H_1: D_{6M} > 0$$

Where D_{6M} is the average change in 6MWT distance from baseline at 6 months.

at the one-sided 2.5% significance level.

2.3.3 Severe MAC Cohort

2.3.3.1 Severe MAC Cohort – Primary Endpoint

The primary endpoint for the Severe MAC Cohort is freedom from all-cause mortality and heart failure hospitalization at 12 months post index procedure.

The null and alternative hypotheses are:

$$H_0: \pi_D \leq \pi_{PG}$$

$$H_1: \pi_D > \pi_{PG}$$

Statistical Analysis Plan

where π_D is the true event rate for the composite of freedom from all-cause mortality and heart failure hospitalization at 12 months and π_{PG} is the performance goal. The performance goal is set at 43% [REDACTED]

[REDACTED]
The null hypothesis will be tested at the one-sided 2.5% level of significance [REDACTED].

The primary analysis population for the primary endpoint is AP population. The primary endpoint will be considered met if the null hypothesis is rejected.

2.3.3.2 Severe MAC Cohort – Secondary Endpoints

The following secondary endpoints will be evaluated. These endpoints will be evaluated for labeling claims if the primary endpoint for the Severe MAC Cohort is met. The primary analysis population for the secondary endpoints of the Severe MAC Cohort is AP population.

2.3.3.2.1 Freedom from MR \leq mild (1+) at 30 days post index procedure

The proportion of subjects with MR \leq mild (1+) at 30 days post the index procedure will be compared to a pre-specified performance goal.

The null and alternative hypotheses are:

$$H_0: P_D \leq P_{PG}$$

$$H_1: P_D > P_{PG}$$

where P_D is the proportion of subjects with MR \leq mild (1+) at 30 days post the index procedure and P_{PG} is the performance goal. The P_{PG} is set at 75%.

one-sided 2.5% significance level. [REDACTED]

2.3.3.2.3 Change in KCCQ from Baseline at 12 months

To evaluate the benefit of the Tendyne device, the Quality of Life as measured by the KCCQ scores at 12 months will be compared with those from baseline.

The null and alternative hypotheses are:

$$H_0: D_{12M} \leq 0$$

Statistical Analysis Plan

$$H_1: D_{12M} > 0$$

Where D_{12M} is the average change in KCCQ score from baseline at 12 months.

at the one-sided 2.5% significance level.

2.3.3.2.3 Improvement of NYHA Functional Classification I or II at 12 months

The proportion of subjects with NYHA Functional Classification I or II at 12 months will be evaluated at two-sided 5% level of significance [REDACTED].

The null and alternative hypotheses are stated as:

$$H_0: P_{M12} = P_B$$

$$H_1: P_{M12} \neq P_B$$

where P_{M12} and P_B represent the proportion of NYHA Classification I or II at 12 months and baseline, respectively.

2.3.3.2.4 Change in Six-Minute Walk Test Distance from Baseline at 12 months

To evaluate the benefit of the Tendyne device, the distance walked at 12 months as measured by the 6MWT will be compared with those from baseline.

The null and alternative hypotheses are:

$$H_0: D_{12M} \leq 0$$

$$H_1: D_{12M} > 0$$

Where D_{12M} is the average change in 6MWT distance from baseline at 12 months.

at the one-sided 2.5% significance level.

Statistical Analysis Plan

2.3.4.2.5 Change in KCCQ from Baseline at 6 months

To evaluate the benefit of the Tendyne device, the Quality of Life as measured by the KCCQ scores at 6 months will be compared with those from baseline.

The null and alternative hypotheses are:

$$H_0: D_{6M} \leq 0$$

$$H_1: D_{6M} > 0$$

Where D_{6M} is the average change in KCCQ score from baseline at 6 months.

at the one-sided 2.5% significance level.

2.3.3.2.6 Change in Six-Minute Walk Test Distance from Baseline at 6 months

To evaluate the benefit of the Tendyne device, the distance walked at 6 months as measured by the 6MWT will be compared with those from baseline.

The null and alternative hypotheses are:

$$H_0: D_{6M} \leq 0$$

$$H_1: D_{6M} > 0$$

Where D_{6M} is the average change in 6MWT distance from baseline at 6 months.

at the one-sided 2.5% significance level.

2.4 Sample Size Calculations

2.4.1 Sample Size Calculation – Randomized Cohort

2.4.1.1 Sample Size Calculation – Randomized Cohort – Primary Endpoint

The sample size, for the Randomized Cohort, is determined based on the primary endpoint of freedom from all-cause mortality and heart failure hospitalizations (HFH) at 12 months. The primary endpoint will be analyzed based on ITT population in which the Tendyne group tested against the MitraClip group for non-inferiority. The null and alternative hypotheses are stated in Section 2.3.1.1.

Statistical Analysis Plan

2.4.1.2 Sample Size Calculation – Randomized Cohort – Secondary Endpoint

2.4.1.2.1 Freedom from MR > mild (1+) at 30 days Post Procedure

The power of the secondary endpoint for the Randomized Cohort, freedom from MR > mild (1+) at 30 days post procedure is also evaluated. The secondary endpoint will be analyzed based on the ITT population in which the Tendyne group tested against the MitraClip. The null and alternative hypotheses are stated in Section 2.3.1.2.

